### **7.2.1. Summaries of Numeric Laboratory Results**

Descriptive statistics (n, mean, SD, median, Q1, Q3, minimum, and maximum) will be provided for ALT, aspartate aminotransferase (AST), total bilirubin, alkaline phosphatase, white blood cell (WBC) counts, neutrophils, lymphocytes, hemoglobin, platelets, reticulocytes, and international normalized ratio (INR) as follows:

- Baseline values
- Values at each postbaseline visit
- Change from baseline at each postbaseline visit

A baseline laboratory value will be defined as the final assessment performed on or prior to the date/time of first dose of study drug. Change from baseline to a postbaseline visit will be defined as the visit value minus the baseline value. The mean, median, Q1, Q3, minimum, and maximum will be displayed to reported number of digits, SD to reported number of digits plus 1.

Median (Q1, Q3) of the observed values for ALT, AST, total bilirubin, alkaline phosphatase, hemoglobin, reticulocytes, WBC, neutrophils, lymphocytes, and platelets will be plotted using a line plot by visit.

In the case of multiple values in an analysis window, data will be selected for analysis as described in Section 3.6.3 (Selection of Data in the Event of Multiple Records in a Window).

The number of subjects with hemoglobin < 10 g/dL and < 8.5 g/dL at any postbaseline visits (up to 30 days after the last dose of any study drug) will be summarized.

### **7.2.2. Graded Laboratory Values**

The Gilead Grading Scale for Severity of Adverse Events and Laboratory Abnormalities will be used for assigning toxicity grades to laboratory results for analysis as Grade 0, Grade 1 (mild), Grade 2 (moderate), Grade 3 (severe), or Grade 4 (potentially life threatening). Grade 0 includes all values that do not meet criteria for an abnormality of at least Grade 1. Some laboratory tests

have laboratory toxicity criteria for both increased and decreased levels; analyses for each direction (ie, increased, decreased) will be presented separately.

#### 7.2.2.1. Treatment-Emergent Laboratory Abnormalities

Treatment-emergent laboratory abnormalities are defined as values that increase at least 1 toxicity grade from baseline at any postbaseline time point, up to and including the date of last dose of study drug plus 30 days for subjects who permanently discontinued study drug, or all available data in the database snapshot for subjects still on treatment at the time of the interim analysis. If the relevant baseline laboratory value is missing, then any abnormality of at least Grade 1 will be considered treatment emergent.

#### 7.2.2.2. Summaries of Laboratory Abnormalities

Laboratory data that are categorical will be summarized using the number and percentage of subjects in the study with the given response at baseline and each scheduled postbaseline visit.

The following summaries (number and percentage of subjects) for treatment-emergent laboratory abnormalities will be provided by analyte; subjects will be categorized according to the most severe postbaseline abnormality grade for a given analyte:

- Graded laboratory abnormalities
- Grade 3 or above laboratory abnormalities

For all summaries of laboratory abnormalities, the denominator is the number of subjects with nonmissing postbaseline values up to 30 days after last dose of study drug for the laboratory parameter of interest.

A by-subject listing of treatment-emergent Grade 3 or above laboratory abnormalities will be provided by subject ID number and visit in chronological order. This listing will include all test results that were collected throughout the study for the analyte of interest, with all applicable severity grades or abnormal flags displayed.

### 7.3. Body Weight, Height, and Vital Signs

Vital signs (systolic and diastolic blood pressure [mmHg], pulse [beats/min]) at each visit, and change from baseline at each visit will be summarized for the safety analysis set using descriptive statistics (n, mean, SD, median, Q1, Q3, minimum, and maximum). The baseline value will be defined as the last available value collected on or prior to the date/time of first dose of study drug. Change from baseline to a postbaseline visit will be defined as the postbaseline value minus the baseline value.

In the case of multiple values in an analysis window, data will be selected for analysis as described in Section 3.6.3 (Selection of Data in the Event of Multiple Records in a Window). No inferential statistics will be generated.

A by-subject listing of vital signs (systolic and diastolic blood pressure [mmHg], pulse [beats/min], respiration [breaths/min], and body temperature [°C]) will be provided by subject ID number and visit in chronological order. In the same manner, a by-subject listing of body weight, height, and BMI will be provided separately.

#### **7.4. Concomitant Medications**

Medications collected at screening and during the study will be coded using the current version of the World Health Organization (WHO) Drug dictionary. The medications will be categorized as prior, concomitant, or both using the following definitions:

- Prior medications: any medications taken prior to the initial study drug dosing date.
- Concomitant medications: any medications initially taken on or after the initial study drug dosing date and within the study drug's treatment period (including study drug's therapeutic reach).
- Prior and concomitant medications: any medications taken both prior to and on or after the initial study drug dosing date and within the study drug's treatment period (including study drug's therapeutic reach); or any medications taken prior to the baseline visit date with a stop date of "continuing".

Concomitant medications will be summarized by preferred name using the number and percentage of subjects. A subject reporting the same medication more than once will be counted only once when calculating the number and percentage of subjects who received that medication. The summary of concomitant medications will be ordered by descending frequency of preferred names. For drugs with the same frequency, sorting will be done alphabetically. For purposes of analysis, any medication with a stop date that is on or prior to the initial study drug dosing date or start date that is after the last study drug dosing date will be excluded from a concomitant medication summary. If a partial stop date is entered, any medication with the month and year (if day is missing) or year (if day and month are missing) prior to the initial study drug dosing date will be excluded from the concomitant medication summary. If a partial start date is entered, then any medication with the month and year (if day is missing) or year (if day and month are missing) after the study drug stop date will be excluded from the concomitant medication summary. Medications with completely missing dates will be included in the concomitant medication summary. Summaries will be based on the Safety Analysis Set. No inferential statistics will be generated.

All prior and concomitant medications (other than per-protocol study drugs) will be provided in a by-subject listing sorted by subject ID number and administration date in chronological order.

#### **7.5. Electrocardiogram Results**

A by-subject listing for ECG assessment results will be provided by subject ID number and visit in chronological order.

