8.6. Safety Analysis

Safety will be evaluated by assessment of clinical laboratory tests (including HIV-1 RNA and CD4 T-cell count for HCV/HIV co-infection subjects), physical examinations, vital signs measurements at various time points during the study, and by the documentation of AEs.

All safety data collected on or after the first dose of study drug administration up to 30 days after the last dose of study drug will be summarized by treatment group according to the study drug received.

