8.7. Other Safety Evaluations

Individual data for 12-lead ECG, vital signs measurements will be listed by subject and summarized by treatment group by incidence of events/abnormalities or descriptive statistical summaries (n, mean, SD, median, Q1, Q3, minimum, and maximum), as appropriate.

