### 3.6.3. Selection of Data in the Event of Multiple Records in an Analysis Window

Depending on the statistical analysis method, single values may be required for each analysis window. For example, change from baseline by visit usually requires a single value, whereas a time-to-event analysis would not require 1 value per analysis window.

If multiple valid nonmissing numeric observations exist in an analysis window, records will be chosen based on the following rules if a single value is needed:

- For baseline, the last available record on or prior to the date of the first dose of study drug will be selected. If there are multiple records with the same time or no time recorded on the same day, average (arithmetic mean) will be used for the baseline value.
- For postbaseline visits:
  - The record closest to the nominal day for that visit will be selected except for HCV RNA posttreatment follow-up visits, for which the latest record in the analysis window will be selected.
  - If there are 2 records that are equidistant from the nominal day, the later record will be selected.
  - If there is more than 1 record on the selected day, the average will be taken, unless otherwise specified.

If multiple valid nonmissing categorical observations exist in a window, records will be selected as follows:

- For baseline, the last available record on or prior to the date of the first dose of study drug will be selected. If there are multiple records with the same time or no time recorded on the same day, the value with the lowest severity will be selected (eg, normal will be selected over abnormal). If multiple ECG measurements occur on the same day prior to the first dose of any study drug, the value with the lowest severity will be selected regardless of the timing of these multiple ECG measurements.
- For postbaseline visits, follow the same rules described above for postbaseline numeric observations, except that if there are multiple records on the same day, the most conservative value will be selected (eg, abnormal will be selected over normal).

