**7.7. Changes From Protocol-Specified Safety Analyses**

There are no deviations from the protocol-specified safety analyses.

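### The SAP cuts the protocol's ECG summary to a listing and specifies no summary of HIV-1 RNA or CD4, yet declares that the safety analyses are unchanged

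*SAP*

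**What the plan says.** **ECG.** Protocol 8.7 states: "Individual data for 12-lead ECG, vital signs measurements will be listed by subject and summarized by treatment group by incidence of events/abnormalities", or by descriptive statistics, whichever suits. SAP 7.5 is a single sentence: "A by-subject listing for ECG assessment results will be provided by subject ID number and visit in chronological order".

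**HIV measures.** Protocol 8.6 opens: "Safety will be evaluated by assessment of clinical laboratory tests (including HIV-1 RNA and CD4 T-cell count for HCV/HIV co-infection subjects"), together with physical examinations, vital signs and adverse events. Its next sentence says that all safety data from the first dose "up to 30 days after the last dose of study drug will be summarized by treatment group according to the study drug received". SAP 7.2.1 names the laboratory tests that get numeric summaries: ALT, AST, total bilirubin, alkaline phosphatase, five blood-count measures, reticulocytes and INR. HIV-1 RNA and CD4 are not among them.

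**Declaration.** SAP 7.7 reads: "There are no deviations from the protocol-specified safety analyses".

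**The concern.** The SAP governs which tables are produced. Where the protocol promises a summary and the SAP provides a listing or nothing, the summary will not be made. Where the SAP's own section on changes says there are none, a reader of the study report has no signal that something was dropped.

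Safety and tolerability of each regimen is a primary objective. Protocol 6.9.7 has end-of-treatment or early-termination ECGs compared with Day 1 as part of routine safety monitoring, so a by-group account of that comparison is the obvious product. Co-infected subjects have HIV-1 RNA and CD4 measured at screening, Day 1, Week 4, Week 8, later four-weekly on-treatment visits where the group has them, and posttreatment Week 4. As the SAP stands, neither body of data reaches a table.

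**Working it through.** No arithmetic applies. The check is a comparison of the two documents.

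**Step 1: ECG.** One sentence in Protocol 8.7 covers both ECG and vital signs. The SAP splits them.

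| Measure | Protocol 8.7 | SAP |
|---|---|---|
| Vital signs | List and summarise by group | 7.3: listing, plus a summary |
| 12-lead ECG | List and summarise by group | 7.5: listing only |

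For blood pressure and pulse, SAP 7.3 says that values "at each visit, and change from baseline at each visit will be summarized for the safety analysis set using descriptive statistics". The summary half of the protocol sentence was therefore kept for vital signs and dropped for ECG.

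SAP 3.6.3 contains a selection rule that begins "If multiple ECG measurements occur on the same day prior to the first dose of any study drug, the value with the lowest severity" and goes on to use that value as the baseline. Such a rule is needed only when a single baseline category per subject is to be tabulated, and no SAP table uses it. The analysis windows in SAP Tables 3-1 and 3-2 cover HCV RNA, vital signs and laboratory data, not ECG.

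**Step 2: HIV-1 RNA and CD4.** There are four places in SAP section 7 where a summary could arise.

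- *SAP 7.2.1, numeric results.* This is a closed list, and neither test is on it.
- *SAP 7.2.2, graded abnormalities.* These tables depend on the grading scale in Protocol Appendix 3. That scale restricts the CD4 grade to HIV-negative adults and adolescents, while CD4 is collected only in co-infected subjects. It has no row for HIV-1 RNA. Neither measure can enter a graded table.
- *SAP 7.2, listings.* Four panels are named: hematology, chemistry, coagulation and urinalysis. None is virology, and listings are not summaries in any case.
- *SAP 7.6, other safety measures.* This covers pregnancies only.

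In the readable text of the SAP, the two tests appear only in the schedule of assessments.

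**Step 3: the declaration.** Protocol 8.7 commits to an ECG summary and Protocol 8.6 commits to summaries of all on-treatment safety data, with HIV-1 RNA and CD4 named as part of them. SAP 7.5 and 7.2 do not deliver these. SAP 7.7 therefore cannot correctly say that there are no deviations.

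**The case against.** **The protocol wording may leave room.** Protocol 8.7 ends by qualifying the summary with a phrase about appropriateness. That phrase follows the choice between incidence and descriptive statistics, and most naturally governs the type of summary, not whether there is one. Even on the looser reading, the change belongs in SAP 7.7.

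**The HIV part is weaker than the ECG part.** This is fair. The sentence naming the two tests promises an evaluation, not a table; the commitment comes from the sentence after it. Protocol 8.6.3, the specific laboratory section, commits only to graded abnormalities, which would yield nothing for HIV. SAP 7.2 says in general terms that laboratory data will be summarised, and SAP 3 promises by-subject listings of collected data. The HIV results would thus probably be listed, but no summary is specified. SAP 6.3 is redacted, so some HIV analysis there cannot be excluded. The safety subsections of SAP section 7 show no redaction.

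**Little is lost.** This largely stands. Under Protocol 7.1.3, abnormal ECGs with signs or symptoms that meet the adverse event definition are recorded as adverse events and so reach the tables in SAP 7.1.6. A reader could also count from the listing by hand.

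A reader might infer four stronger points, none of which the documents support:

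- *HBV DNA is a further deviation.* It is collected in HBcAb-positive subjects and appears in no readable SAP analysis, but no analysis section of the protocol names it. Only the generic references to laboratory tests and safety data could bring it in.
- *Confidence limits on ECG worsening are lost.* Neither document plans confidence intervals for safety data, and no group sizes are given. The protocol's own ECG summary would not supply such limits.
- *The high GS-331007 exposure makes the omission serious.* Protocol 1.2.3 and 1.5 tie that exposure to reduced red cells. SAP 7.2.1 summarises hemoglobin and reticulocytes and counts subjects below 10 and 8.5 g/dL.
- *A count of HIV virologic rebound is a missing endpoint.* The definition in Protocol 3.5 serves subject management. It is neither an endpoint nor a planned analysis.

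**Conclusion.** Wrong as written, minor. The ECG contradiction is plain: the protocol requires a listing and a group summary, the SAP gives a listing, and SAP 7.7 denies any change. The HIV contradiction also holds, but it rests on reading the two sentences of Protocol 8.6 together and on readable SAP text only.

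The primary safety endpoint, adverse events leading to permanent discontinuation of study drug, is unaffected, as are all adverse event tables. The practical loss is mainly two things: by-group counts of ECG changes that were not reported as adverse events, and a summary of HIV-1 RNA and CD4 over time. The number of co-infected subjects is not stated, so how informative the second would be is unknown.

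**What to change.** 1. **SAP 7.5.** Add the number and percentage of subjects in each ECG assessment category at Day 1 and at end of treatment or early termination, by treatment group and overall. A shift table between the two visits would serve equally. Use the categories recorded on the eCRF, since the protocol and SAP do not define a scale.
2. **SAP 7.2.** For HIV co-infected subjects, add descriptive summaries of HIV-1 RNA and CD4 by visit, with change from baseline for CD4, by treatment group within the window of last dose plus 30 days.
3. **SAP 7.7.** Correct the statement. If the sponsor prefers to keep ECG or HIV data as listings only, say so there and give the reason.

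The cost is a few small descriptive tables from assessments already in the schedule, or a short paragraph in SAP 7.7. No change to data collection or sample size is needed.

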**7.6. Other Safety Measures**

A data listing will be provided for subjects who become pregnant during the study.

**7.7. Changes From Protocol-Specified Safety Analyses**

There are no deviations from the protocol-specified safety analyses.

## 8. PHARMACOKINETIC ANALYSES

Plasma concentrations of SOF (and its metabolites GS-566500 and GS-331007) and LDV in plasma will be determined using validated bioanalytical assays.

Population PK models for SOF, GS-331007 and LDV, previously developed for the Phase 2/3 LDV/SOF US NDA population analyses, will be applied to the data from all PK samples collected in this study. Details of the population PK analysis will be provided in a separate population PK analysis plan.

The systemic concentration of study drug prior to and immediately following hemodialysis will also be summarized using descriptive summary statistics (sample size, mean, SD, coefficient of variation [%CV], median, Q1, Q3, minimum, maximum). For concentration values BLQ, the number of subjects with values of BLQ will be presented.

CCI

## **10. SOFTWARE**

SAS® Software Version 9.4. SAS Institute Inc., Cary, NC, USA.

WinNonlin® Phoenix® software v6.3 (Pharsight Corporation, Mountain View, CA).

## 11. SAP REVISION

## 12. APPENDICES

### Appendix 1 Schedule of Assessments

**Appendix 1 Schedule of Assessments**

**Appendix Table 1. Screening/Baseline/ On-Treatment and Post Treatment Study Visits for Group 1**

	Screen	Baseline/Day 1 a	On-treatment Study Week ( $\pm 3$ days)				Post treatment Study Week ( $\pm 5$ days) i		
			2	4	6	8/ET	4	12	24
Informed Consent	X								
Determine Eligibility	X	X							
Medical History	X								
Physical Examination	X	X				X	X	X	X
Height	X								
Weight	X	X				X			
Vital Signs	X	X	X	X	X	X	X	X	X
12-Lead ECG	X	X				X			
AEs /SAE b	X	X	X	X	X	X	X	X b	X b
Concomitant Medications	X	X	X	X	X	X	X		
Pregnancy Prevention Counseling	X	X		X		X	X		
Health Related Quality of Life c		X				X		X	
Review of Study Medication Compliance			X	X	X	X			
Study Drug Dispensing d		X		X					
Laboratory Assessments									
Hematology, Chemistry	X	X	X	X	X	X	X	X	X
Coagulation Tests	X	X				X			
HCV RNA	X	X	X	X	X	X	X	X	X

	Screen	Baseline/Day 1 a	On-treatment Study Week ( $\pm$ 3 days)				Post treatment Study Week ( $\pm$ 5 days) i		
			2	4	6	8/ET	4	12	24
Viral Sequencing/Phenotyping e		X	X	X	X	X	X	X	X
Sparse PK			X	X	X	X			
Intensive PK g,h					X h	X h			
Hemodialysis PK g,i					X i	X i			
Serum $\beta$ -hCG Pregnancy Test j	X	X		X		X	X		
Serum Drug Screen	X								
HCV & IL28B Genotyping	X								
HCV, HIV, HBV Serology	X								
HBV DNA k		X		X		X	X	X	X
HbA1c	X								
Fibrotest ®	X								
Archive Sample f		X				X			
Pharmacogenomic Sample f		X							
CD4 Cell Count l	X	X		X		X	X		
HIV-1 RNA l	X	X		X		X	X		

a Baseline/Day 1 assessments must be performed prior to dosing

b Only SAEs will be collected at post-treatment Weeks 12 and 24.

c Health Related Quality of Life (HRQoL) Surveys (e.g., SF-36, CLDQ-HCV, FACIT-F and WPAI) will be conducted for all subjects where the surveys are available at Day 1, Week 8, ET (if applicable), and posttreatment Week 12.

d The IWRS will provide direction on the specifics of each subject's study drug dispensing

e. Plasma samples will be collected for possible viral resistance testing and other virology studies

f Subjects may opt out of archive/pharmacogenomics sample collection.

g Only for subjects who have provided consent for this sample and testing.

h Intensive PK evaluations will be assessed at the following timepoints: 0 (pre-dose -5 minutes), 0.25, 0.5, 1, 2, 4, 6, 8, 10, and 12 hours post dose once either on Week 6 or 8, per investigator discretion.

- i Hemodialysis PK blood samples will be collected at one hemodialysis session between Week 6 and Week 12, inclusive (as appropriate based on treatment group), evaluations will include: 1. A single blood sample will be collected within 10 minutes before hemodialysis initiates. 2. During hemodialysis, a single sample will be collected from both the arterial and venous sides of the dialyzer within 1 hour of hemodialysis concluding. 3. Finally, a single blood sample will be collected within 10 minutes after hemodialysis concludes.
- j For females of child bearing potential only
- k Only for subjects who are HBcAb+ at Screening
- l For HIV/HCV co-infected subjects only.

**Appendix Table 2. Screening/Baseline/ On-Treatment and Post Treatment Study Visits for Group 2**

	Screen	Baseline/Day 1 a	On-treatment Study Week ( $\pm$ 3 days)					Post treatment Study Week ( $\pm$ 5 days) i		
			2	4	6	8	12/ET	4	12	24
Informed Consent	X									
Determine Eligibility	X	X								
Medical History	X									
Physical Examination	X	X					X	X	X	X
Height	X									
Weight	X	X					X			
Vital Signs	X	X	X	X	X	X	X	X	X	X
12-Lead ECG	X	X					X			
AEs /SAE b	X	X	X	X	X	X	X	X	X b	X b
Concomitant Medications	X	X	X	X	X	X	X	X		
Pregnancy Prevention Counseling	X	X		X		X	X	X		
Health Related Quality of Life c		X					X		X	
Review of Study Medication Compliance			X	X	X	X	X			
Study Drug Dispensing d		X		X		X				
Laboratory Assessments										
Hematology, Chemistry	X	X	X	X	X	X	X	X	X	X
Coagulation Tests	X	X					X			
HCV RNA	X	X	X	X	X	X	X	X	X	X
Viral Sequencing/Phenotyping e		X	X	X	X	X	X	X	X	X

	Screen	Baseline/Day 1 a	On-treatment Study Week ( $\pm$ 3 days)					Post treatment Study Week ( $\pm$ 5 days) i		
			2	4	6	8	12/ET	4	12	24
Sparse PK			X	X	X	X	X			
Intensive PK g,h					X h	X h	X h			
Hemodialysis PK g,i					X i	X i	X i			
Serum $\beta$ -hCG Pregnancy Test j	X	X		X		X	X	X		
Serum Drug Screen	X									
HCV & IL28B Genotyping	X									
HCV, HIV, HBV Serology	X									
HBV DNA k		X		X		X	X	X	X	X
HbA1c	X									
Fibrotest ®	X									
Archive Sample f		X					X			
Pharmacogenomic Sample f		X								
CD4 Cell Count l	X	X		X		X	X	X		
HIV-1 RNA l	X	X		X		X	X	X		

a Baseline/Day 1 assessments must be performed prior to dosing

b Only SAEs will be collected at post-treatment Weeks 12 and 24.

c Health Related Quality of Life (HRQoL) Surveys (e.g., SF-36, CLDQ-HCV, FACIT-F and WPAI) will be conducted for all subjects where the surveys are available at Day 1, Week 8, ET (if applicable), and posttreatment Week 12.

d The IWRS will provide direction on the specifics of each subject's study drug dispensing

e Plasma samples will be collected for possible viral resistance testing and other virology studies

f Subjects may opt out of archive/pharmacogenomics sample collection.

g Only for subjects who have provided consent for this sample and testing.

h Intensive PK evaluations will be assessed at the following timepoints: 0 (pre-dose -5 minutes), 0.25, 0.5, 1, 2, 4, 6, 8, 10, and 12 hours post dose once either on Week 6 or 8, per investigator discretion.

- i Hemodialysis PK blood samples will be collected at one hemodialysis session between Week 6 and Week 12, inclusive (as appropriate based on treatment group), evaluations will include: 1. A single blood sample will be collected within 10 minutes before hemodialysis initiates. 2. During hemodialysis, a single sample will be collected from both the arterial and venous sides of the dialyzer within 1 hour of hemodialysis concluding. 3. Finally, a single blood sample will be collected within 10 minutes after hemodialysis concludes.
- j For females of child bearing potential only
- k Only for subjects who are HBcAb+ at Screening
- l For HIV/HCV co-infected subjects only.

